## 7.8 Dose Adjustments

### 7.8.1 Dose Escalation Beginning at Week 4

The initial dose of fostamatinib will be 100 mg PO *bid* or matching placebo.

Starting at Week 4, the initial fostamatinib dose of 100 mg PO *bid* or matching placebo will be increased to fostamatinib 150 mg PO *bid* or matching placebo if subjects have adequately tolerated the study drug in the investigator's judgment.

### 7.8.2 Dose Adjustments Due to Adverse Events

Clinical testing to date has identified adverse events that may require temporary interruption of the study drug and/or a reduction in study drug dose. Modification of study drug administration may be required under the following circumstances (see [Appendix 2](#) for guidance regarding AE-related dose adjustments):

- Increases in ALT or AST;
- ANC <1000 / mm^3;
- Severe diarrhea;
- Hypertension; or
- Severe or life-threatening adverse events considered to be related to study drug administration.

Subjects who have their dose reduced may be considered for a re-escalation of the study drug dose following resolution of the AE the required the dose reduction, only after consultation with the Medical Monitor. If a subject experiences additional dose-limiting AEs, the dose of study drug may be further reduced to a dose as low as 100 mg *qd*.

Subjects whose dose reduction results in a once daily dose of fostamatinib will take the daily study drug dose in the morning. [Table 5](#) details the strategy for dose adjustment in subjects who experience AEs requiring dose reduction. [Appendix 2](#) provides the recommended dose modifications for specific adverse events.

**Table 5: Dose Adjustment**

Starting Dose	Dose Level -1	Dose Level -2	Dose Level -3	Dose Level -4
100 mg PO bid	150 mg PO qd	100 mg PO qd	discontinue	----
150 mg PO bid	100 mg PO bid	150 mg PO qd	100 mg PO qd	discontinue

## 7.9 Rescue Protocol

Use of rescue medications including increases in steroid doses should be avoided for the duration of the study unless medically necessary. Rescue may be given following a decrease in Hgb of  $>1.5$  g/dL from baseline **OR** new or worsening symptoms of anemia, so long as urgent treatment is required in the judgment of the Investigator. In subjects meeting these criteria, the following rescue regimens are permitted:

1. Increase or initiate steroid dose up to 80 mg/daily prednisone (or equivalent) for approximately 2 weeks or until clinically stable, then taper the dose by 10 to 20 mg prednisone (or equivalent) per week until return to baseline dose level (see [Appendix 3](#) for prednisone equivalents conversion table);
2. IV methylprednisolone up to 1 g/day x 1 day up to 3 days;
3. Oral dexamethasone up to 40 mg/day x up to 4 days;
4. Red blood cell (RBC) transfusion;
5. IVIg: up to 1g/kg x 1 day up to 3 days.

The Investigator must discuss all instances of rescue therapy with the Sponsor's Medical Monitor in advance of initiating the therapy whenever possible. The use of any rescue therapy regimen not noted above is not permitted. Only the rescue regimens above are allowed.

## 7.10 Steroid Taper Protocol:

For subjects who have reached Week 12, achieved a durable response and have had at least 2 subsequent *scheduled* visits with hemoglobin assessments showing continued response, a steroid taper may be considered as follows:

- If the dose is above 20 mg/day prednisone (or equivalent), decrease dose level by 10 mg\* (or equivalent) every other week, until the dose level is 20 mg/day prednisone (or equivalent). Then decrease the dose by 5 mg increments every other week until the dose is 10 mg/day and maintain. See [Appendix 3](#) for prednisone equivalents conversion table.
- The taper may be suspended at any dose level to maintain the hemoglobin response and as needed for subject safety (e.g., to avoid adrenal insufficiency).
- If a decrease in hemoglobin of  $\geq 0.5$  g/dL is observed at any subsequent visit (as compared to either the last hemoglobin obtained prior to initiating the taper **OR** the previous hemoglobin assessment), the current steroid dose level should be maintained and the hemoglobin repeated in 3 days to assure no recurrence of hemolysis. A sustained (at least 2 consecutive hemoglobin results) decrease in hemoglobin of  $\geq 1.0$  g/dL should prompt a re-escalation of prednisone (or equivalent) dose to the previous, higher dose level.

- If the steroid dose is 10 mg/day prednisone (or equivalent) or below, no steroid tapering is allowed in this study.

\*If the steroid dose is 25 mg/day of prednisone or equivalent, decrease the dose by 5 mg increments to 10 mg/day and maintain. For example, if the dose is 35 mg/day of prednisone or equivalent (or higher dose that is a multiple of 5), decrease the dose in 10 mg increments as described above to 25 mg/day for 2 weeks; then decrease in 5 mg increments to 10 mg/day and maintain.

**Consideration of a steroid taper is to be discussed with the Medical Monitor prior to initiating any changes.**

### **7.11 Concomitant Erythropoietin Stimulating Agents**

In subjects meeting the above response criteria (durable response and 2 subsequent scheduled visits with hemoglobin showing continued response); if the hemoglobin increases to above the upper limit of normal the ESA dose may be reduced by 50% every 4 weeks.

### **7.12 Missed Doses/Dose Interruptions**

Missed doses will be considered as a dose interruption if the prescribed doses have been missed for two or more consecutive days.

Restarting study drug after interruption may require performance of procedures for safety that were missed during the interruption. The Medical Monitor should be consulted when considering study drug restart after a prolonged interruption (e.g., > 2 weeks).

### **7.13 Definition of Study Procedures**

#### **7.13.1 Medical History**

The following documentation will be collected at screening and reviewed at baseline (Day 1):

- Medical/surgical history
- The date/year of AIHA diagnosis
- All previous treatments for AIHA
- Active AIHA treatment

#### **7.13.1.1 Physical Exam**

A complete physical exam will be done at screening and Week 24/ET and should include evaluation of the head, eyes, ears, nose, and throat (HEENT), cardiovascular, dermatological, musculoskeletal, respiratory, gastrointestinal, and neurological systems as well as an assessment of KPS. Height and weight will be collected at screening. Weight will be collected again at Week 12 and Week 24/ET. Abbreviated physical examinations will be performed as per the study

schedule in [Table 4](#). Prior to initiation of treatment, any new or worsened abnormalities should be recorded as medical history. Following the initiation of study treatment, any clinically significant new or worsened abnormalities will be recorded as adverse events.

### **7.13.1.2 Karnofsky Performance Status Assessment**

The KPS (see [Appendix 1](#)) is a widely used method of assessing the functional status of patients. KPS score will be collected as part of the eligibility criteria. The KPS describes the patient's functional status using percentage value ranges from 100% (no evidence of disease) to 0% (death).

### **7.13.1.3 Vital Signs**

Vital signs (blood pressure, pulse, and temperature) will be assessed at all study visits. All blood pressure determinations should be made with the subject seated and taken after the subject rests for 5 minutes.

If the initial blood pressure at any visit other than screening is  $\geq 130$  mmHg systolic or  $\geq 80$  mmHg diastolic, the subject should remain seated and the blood pressure should be taken 2 additional times at least 3 minutes apart. If the average of the 3 measurements is  $\geq 130$  mmHg systolic or diastolic is  $\geq 80$  mmHg, follow the guidelines in [Appendix 2](#).

### **7.13.2 Questionnaires**

The FACIT-F and EQ-5D-5L subjects' reported outcomes (PRO) will be administered at Baseline, Week 12 and Week 24 (Early Termination). The subject is to read questionnaire by him/herself and write/mark answers directly onto the questionnaire. Questionnaires should be checked for completeness only.

### **7.13.3 Electrocardiogram**

A 12-lead ECG will be obtained after 5 minutes of rest in the supine position using equipment at the site at screening. The Investigator or designee will evaluate the ECG for abnormalities.

### **7.13.4 Laboratory Tests**

Laboratory samples will be collected, processed, shipped and managed according to the lab manual. Samples will be obtained at each study visit according to the schedule in [Table 4](#). The total amount of blood collected for the duration of the 24-week study and 28-day screening period study is approximately 200 mL.

The following tests are to be collected and analyzed for the study:

- DAT specific for anti-IgG. Eligibility may be based on a historical DAT obtained within 12 months of the screening visit from a local laboratory, provided that specific IgG positivity is documented; otherwise, this assay will be done at screening by a central laboratory;

- Haptoglobin;
- Hematology: hemoglobin; red blood cell count (RBC); white blood cell count (WBC), platelet count, hematocrit, WBC differential count (neutrophils, lymphocytes, eosinophils, monocytes, and basophils), mean corpuscular hemoglobin concentration (MCHC), mean corpuscular hemoglobin (MCH), mean corpuscular volume (MCV), mean platelet volume (MPV), and red blood cell distribution width (RDW);
- Serum Chemistry: includes Na, K, Cl, bicarbonate (CO2), Ca, PO4, blood urea nitrogen (BUN), creatinine, globulin, random glucose, LDH, AST, ALT, alkaline phosphatase, total bilirubin, direct and indirect bilirubin, total protein, albumin;
- Reticulocyte count;
- Liver Function Tests: includes ALT, AST, alkaline phosphatase, LDH, total, direct and indirect bilirubin; and
- Urinalysis (UA): appearance, glucose, ketones, blood, protein, nitrate, bilirubin, specific gravity, pH, urobilinogen, and leukocytes. A microscopic urinalysis will be performed if protein, leukocyte esterase, blood, or nitrite are abnormal.

An abnormal laboratory value is clinically significant if it meets any of the following criteria, and as such should be documented on the AE page of the eCRF:

- Test result is associated with accompanying symptom;
- Test result requires additional diagnostic testing or medical/surgical intervention;
- Test result leads to change in study drug dosing or discontinuation from the study, significant additional concomitant drug treatment, or other therapy; or
- Test result is considered an AE by the Investigator or Sponsor.

Any laboratory result abnormality fulfilling the criteria for an SAE should be reported as such, in addition to being recorded as an AE.

All subjects' laboratory results with clinically significant abnormal values should be followed regularly until the values return to the normal range or until a more plausible alternative cause, other than drug-related AE(s), is identified.

#### **7.13.5 Pregnancy Tests**

Serum pregnancy tests will be performed by the central laboratory for all female subjects of childbearing potential at the screening and baseline visits and then monthly during the study. Subjects who have a confirmed positive pregnancy test at any time during the study will be discontinued from further study drug administration and will be followed for safety (see [Section 9.4](#)).

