## 7.2 Baseline/Day 1/First Dose (Day 1/Week 0)

The Baseline/First Dose visit will occur within 28 days after screening.

To be eligible for enrollment in the study, subjects must have met all inclusion/exclusion criteria at the baseline visit prior to first dose.

The Medical Monitor must review and approve each subject's eligibility verification form prior to randomization.

The following assessments will be completed prior to study drug administration:

- Changes in medical history
- FACIT-F and EQ-5D Questionnaires: Subject is to read questionnaire by him/herself and write/mark answers directly onto the questionnaire
- Abbreviated physical examination
- Concomitant Medications
- Vital Signs (blood pressure, pulse, and temperature)
- Hemoglobin level and reticulocyte count
- CBC, differential, and platelet count
- Serum Chemistry (with LFTs)
- Haptoglobin
- XXXXXXXXXX (see [Section 7.13.7](#))

---

 NOTE: If the initial blood pressure at any visit is  $\geq 130$  mmHg systolic or  $\geq 80$  mmHg diastolic, the subject should remain seated and the blood pressure should be taken at least 2 additional times at least 3 minutes apart. If the average of the 3 measurements is  $\geq 130$  mmHg systolic or  $\geq 80$  mmHg diastolic, follow the guidelines in [Appendix 2](#).

- Urinalysis
- Serum pregnancy test (for females of childbearing potential)
- Randomize for drug assignment in RTSM system

All subjects start the study at the 100mg dose. The first dose of study drug should be administered in the clinic to ensure that the subject understands dosing instructions. For all subjects, this dose will be considered the evening dose for this day no matter what time it is administered. Study staff will instruct the subject to take the study drug *bid* beginning the following morning. See [Section 8.4](#) for additional information regarding study drug dispensation and administration.

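### The pregnancy test due before the Day 1 dose goes only to the central laboratory, so unless that laboratory reports the same day it cannot decide whether the dose is given

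*Combined protocol and SAP*

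**What the plan says.** Section 7.2 sets the rule for Day 1: "To be eligible for enrollment in the study, subjects must have met all inclusion/exclusion criteria at the baseline visit prior to first dose". Inclusion criterion 9 in Section 6.1 makes not being pregnant one of those criteria. Unlike the hemoglobin criterion, it is not tied to the screening visit.

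Section 7.2 then opens its Day 1 list with "The following assessments will be completed prior to study drug administration". The serum pregnancy test is on that list, and the item after it is "Randomize for drug assignment in RTSM system". Dosing follows at the same visit: "The first dose of study drug should be administered in the clinic to ensure that the subject understands dosing instructions". For scheduling purposes, "this dose will be considered the evening dose for this day no matter what time it is administered".

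Section 7.13.5 names who runs the test: "Serum pregnancy tests will be performed by the central laboratory for all female subjects of childbearing potential at the screening and baseline visits". For a positive result it says: "Subjects who have a confirmed positive pregnancy test at any time during the study will be discontinued from further study drug administration". Section 7.13.4 has laboratory samples shipped and handled under the lab manual. The synopsis describes multiple international sites.

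Table 4 schedules only a serum pregnancy test, at screening, Day 1, every four weeks to Week 24, and at follow-up. Footnote h limits it to women of childbearing potential. Table 4 marks the inclusion/exclusion check at screening only.

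**The concern.** The protocol asks for a second pregnancy test on the day of first dosing, in addition to the one at screening. Such a test prevents exposure only if its result is known before the tablet is swallowed. A result from a shipped sample may well arrive after the visit has ended. The test would then be drawn in time but read too late.

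The Day 1 test is the last that can prevent fetal exposure; every later test can only shorten it. The protocol takes such exposure seriously. Section 9.4 requires drug to be stopped immediately, notification within 24 hours and follow-up of a newborn to 30 days. What is at stake is participant safety and a clear instruction to sites.

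**Working it through.** There is no figure in the plan to reproduce. The check sets the provisions side by side and then sizes the consequence.

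**Step 1: is a result needed before dosing?** Section 7.2 requires eligibility to be met and the test completed before study drug. The natural reading is that the result comes first. If completed means only that blood has been drawn, the Day 1 test plays no part in the decision to dose, and eligibility on this criterion rests on screening.

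**Step 2: can the stated method deliver it?**
- Laboratory: central (7.13.5).
- Transport: shipped (7.13.4).
- Turnaround: not stated.
- Local or urine pregnancy test: not provided for.
- Permission to draw the Day 1 sample early: not stated.
- Local laboratories elsewhere: accepted for hemoglobin (10.3.6) and historical DAT (6.1, item 2). Appendix 7 allows local laboratory checks for on-study visits during a pandemic, but does not extend this to the Day 1 pregnancy test.

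The method therefore works only if a shipped sample is reported the same day. The documents neither confirm nor exclude that.

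**Step 3: age of the last known negative.** Screening runs from Day -28 to Day -1. If the Day 1 result is not available, the last negative is 1 to 28 days old. Section 7.1.1 allows screening assessments to be repeated up to two more times in the window, so it can be kept near the lower end.

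**Step 4: illustrative exposure.** Assume that the result is read d days after the draw, after that morning's tablet, and that the site has not waited. The clinic dose is the only Day 1 dose, and twice-daily dosing starts the next morning. For d of 1 or more:

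doses before the result = 1 + 2 × (d − 1) + 1 = 2d, at 100 mg each.

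| Assumed d | Doses | Total | Share of 56 |
|---|---|---|---|
| 0, site waits | 0 | 0 mg | 0% |
| 1 | 2 | 200 mg | 3.6% |
| 2 | 4 | 400 mg | 7.1% |
| 3 | 6 | 600 mg | 10.7% |

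The comparator is the number of doses due by the next scheduled test, at Week 4 (nominally Day 29): 1 + 2 × 27 + 1 = 56. Even with a delay of some days, the Day 1 test would cut exposure well below that of waiting for Week 4. It would not prevent exposure.

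**The case against.** The strongest reply is that the rule is already written. Section 7.2 forbids dosing anyone who does not meet the criteria, so a site that doses without a result departs from the protocol, and the exposures in the table assume that departure. The Medical Monitor must also approve an eligibility form before randomization. The lab manual may provide a rapid result, and leaving logistics to a manual is ordinary practice. The remaining risk needs a pregnancy that begins or becomes detectable after a negative screening test, despite highly effective contraception (for hormonal methods, at least 30 days of consistent use before screening).

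Much of this stands. It limits the size of the problem and makes it conditional on turnaround. It does not remove it: the protocol states the requirement and names a method that may be unable to meet it. The contents of the eligibility form are not supplied, so it is unknown whether the form asks for the Day 1 result.

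Three stronger readings might be inferred, and the documents do not support them.
- *Sites must either dose on a four-week-old result or give up same-visit dosing.* They have other routes. They can repeat the screening test shortly before Day 1, wait until later in the day (the clinic dose counts as the evening dose at any hour), or add a local test, which nothing forbids.
- *The wording about further study drug in Section 7.13.5 shows that the Day 1 test has no role before dosing.* That sentence covers positives at any time in the study. Exclusion before dosing is handled by Sections 6.1 and 7.2.
- *The protocol permits dosing of pregnant women.* It does not; criterion 9 and Section 7.2 exclude them.

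**Conclusion.** The point holds in conditional form. As specified, the Day 1 test cannot decide whether the Day 1 dose is given unless the central laboratory reports a shipped sample the same day. If it does not, the last known negative is the most recent screening result, 1 to 28 days old.

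The main assumption is that no same-day central result is available. International sites and shipped samples make this plausible, but the lab manual could show otherwise. The number of women of childbearing potential among the approximately 90 subjects is not given, so no event rate can be derived. Remaining cases would mostly need contraceptive failure or non-adherence, and exposure would be short.

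This is an inexpensive safety improvement. It does not touch the sample size or the primary analysis, and nothing here suggests that the trial's conclusions would be at risk.

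**What to change.** In Section 7.2, Section 7.13.5 and Table 4 footnote h, require a negative local pregnancy test on Day 1, read before randomization and first dose. A urine dipstick would do, since urine is already collected that day for the urinalysis. Keep the central serum test as confirmation. If the lab manual already secures a same-day result, one sentence in Section 7.2 saying that the negative result must be in hand is enough.

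The cost is one inexpensive test per woman of childbearing potential. Table 4 already schedules 8 central serum tests (screening, Day 1, and Weeks 4, 8, 12, 16, 20 and 24), or 9 with Week 26 for those not entering the extension. Wording changes in three places, and randomization is occasionally delayed while a false positive is resolved. No extra invasive procedure is needed.

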### 7.13.6 Pharmacokinetic Samples

Plasma will be collected according to the schedule in [Table 4](#) for PK analysis. PK will be drawn at the Week 2, 4, 12, and 18 visits. The timing of the PK sampling as well as the date and time of the last dose of study drug will be recorded. Subjects are not required to take study drug in the clinic the day the sample is collected. Samples will be shipped to and stored at the central laboratory at -70°C during the course of the study. Samples will then be transferred to and analyzed at the corresponding bioanalytical laboratory.

After completion of the study, samples may be stored for an additional 5 years for further metabolite identification and/or evaluation of the bio-analytical method in relation to this study. Data from these analyses will be used by Rigel for internal research purposes related to this study and will not be included in the clinical report. All samples will be destroyed after analysis or expiration of the 5-year time period.

### 7.13.7

[REDACTED]

[REDACTED]

### 7.14 Concomitant, Allowed and Restricted Therapies

Concomitant therapies will be recorded in the eCRF at the Screening Visit (for all concomitant therapies 30 days prior to baseline) through Week 24.

#### 7.14.1 Allowed AIHA Therapies

Subjects may continue concurrent steroid therapy and other wAIHA therapy (maximum of 2 therapies) as listed below throughout their participation in the study (note: throughout this document the term 'steroid' indicates corticosteroid drugs as well as glucocorticoids). If an allowed medication is discontinued during screening, the interval between last dose of medication and randomization must meet the time frames listed in the table below:

Medication	Number of weeks required to be at stable dose prior to randomization	Minimum required interval between discontinuation and randomization
Azathioprine	4 weeks	4 weeks
Steroids, including dexamethasone	2 weeks	2 weeks
Erythropoiesis-stimulating agents	4 weeks	4 weeks
Mycophenolate Mofetil	4 weeks	4 weeks
Dapsone	4 weeks	4 weeks
Danazol	4 weeks	4 weeks

Doses and regimens of concurrent wAIHA therapies allowed at entry may not be changed during the 24-week treatment period except for temporary steroid dose increases instituted as rescue therapy or a steroid taper as allowed by the protocol (see [Section 7.9](#) for Rescue Protocol and [Section 7.10](#) for Steroid Taper Protocol).

If Promacta is being given as a concurrent medication, the dose must be stable for 4 weeks prior to randomization.

Splenectomy and other medications when prescribed for wAIHA (e.g., rituximab or other anti-CD20 monoclonal antibody, cyclosporine, ibrutinib or other BTK inhibitor, chemotherapy agents such as cyclophosphamide, vincristine, investigational agents for AIHA, etc.) are not allowed during study treatment (from Day 1 until the last dose of study drug). Subjects requiring any AIHA therapies other than those allowed, or an escalation of the allowed medications other than steroids should be withdrawn from the study. The Medical Monitor should be consulted in these instances.

